11. SURVEILLANCE ON MEDICAL DEVICES

Since the medical devices under study are CE marked and used in accordance with the intended use indicated by the Manufacturer, the surveillance will be carried out in accordance with the provisions for post-market investigations (MEDDEV 2.12.1 - Guidelines on a medical devices vigilance system): the specific definitions of adverse event and reporting obligations will therefore be applied and in compliance with the company Procedure "Supervision of medical devices, active implantable medical devices, in vitro diagnostic devices" (PRDMVIG01 of 12/01/2015).

In accordance with the provisions of the Meddev 2.7-3 guideline (Guidelines on medical devices clinical investigations: serious adverse event reporting), any safety reports will be notified to the Ethics Committee.

11.1 Security Definitions

Accident definition: an accident / near miss is any malfunction or deterioration of the characteristics and / or performance as well as any deficiency in the labeling or in the instructions for use of a device which, directly or indirectly, may cause or have caused death or serious injury. worsening of the state of health of the patient or of a user or other people.

Any event that meets all three of the basic detection criteria listed below is considered an accident and must be reported to the National Competent Authority.

- **An event happened**

This also includes situations in which, following tests performed on the device or following the analysis of the information provided with the device or any other scientific information, factors emerge that could lead or have led to an event. Typical events include, but are not limited to:

- a. a malfunction or deterioration in characteristics or performance (a malfunction or deterioration must be interpreted as an inability of the device to operate in accordance with its intended use, even if the device is used according to the manufacturer's instructions);
- b. false positive or false negative test results that are outside the stated performance limits of the test;
- c. unexpected adverse reactions or unexpected side effects;
- d. interactions with other substances or products;
- e. degradation / destruction of the device;
- f. inappropriate therapy;

- g. lack of accuracy in labeling, instructions for use and / or promotional material. Lack of accuracy includes omissions and deficiencies. Omissions do not include the absence of information that should be well known to the intended user.
- **It is suspected that the manufacturer's medical device is a contributing cause of the accident**

In assessing the link between the device and the accident / missed accident, the Investigator or other healthcare professional must take into account:

- a. the opinion, based on available evidence, of health professionals;
 - b. evidence of similar incidents that occurred previously;
 - c. the results of the manufacturer's preliminary assessment;
 - d. other evidence held by the manufacturer;
 - e. if the judgment is difficult and in complex circumstances it must be assumed that the device may have caused or contributed to causing the accident and that the manufacturers have not paid due caution.
- **The event caused, or could have caused the death or serious deterioration of the state of health (of the patient, user or other person)**

Severe deterioration in health can mean:

- a. a serious illness;
- b. permanent impairment of a bodily function or permanent damage to a bodily structure;
- c. a condition that requires medical or surgical intervention to prevent cases (a) or (b);
- d. any indirect damage resulting from the onset of incorrect diagnostic results or IVD tests, when used in compliance with the manufacturer's instructions for use;
- e. fetus distress, fetus death, or any congenital anomalies or birth defects.

PLEASE NOTE: It should be noted that not all accidents involve a risk and / or cause death or serious deterioration of the state of health (of the patient, user or other person). The non-occurrence of this outcome may be due to other circumstances or the intervention of the healthcare professional. It is therefore sufficient that an accident associated with a device has occurred, and that the accident was such that, if it recurs, it could lead to death or serious deterioration of health (of the patient, user or other person).

11.2 Timing for reporting an Incident

The reporting of an accident by the Investigator or other health professionals must take place immediately after the occurrence of the accident / missed accident, to allow compliance with the transmission times to the Ministry, or within a maximum of 10 days.

The report must be sent signed by the Investigator to the contact person for the surveillance device (RAV) of Active Medical Devices and Health Equipment of CND Y and Z class, completing the report form (Attachment), available on the company intranet in a complete and legible way following the path: Portal Home> Medical Devices Company Commission> MEDICAL DEVICES SURVEILLANCE.

*Contact person for the supervision of the
Active Medical Devices and health equipment of CND Y and Z class*

Ing. [name]

[contact]

[contact]

E-mail: [contact]

For 10 days following the submission of the report, the medical device must remain available to the competent authority. After this deadline, the medical device subject to reporting must be entrusted to the RAV subject to agreements with the same for the times and methods of delivery.

11.3 Forwarding of the report to the Competent Authority and to the Ethics Committee

The RAV provides for the transmission of the complete Accident Form signed by the Investigator, together with a cover letter, to the Ministry of Health at Office V of the General Directorate of Medical Devices and Pharmaceutical Service (DGDMF). This documentation will also be sent to the local Ethics Committee.

The RAV will transmit the appropriate feedback information to the reporter, the PI of the study and the Local Ethics Committee.

11.4 Urgent security measures

Any communications relating to safety notices and / or recall on medical devices in use within the study, communicated by the Manufacturer and / or Competent Authority and received by the RAV, will be sent to the IP of the study and to the provincial Ethics Committee and to the internal board (for safety assessment).

12. STATISTICAL ASPECTS

12.1 The champion

The study is proposed as an exploratory, prospective, experimental and monocentric study.

Regarding the main endpoint (toxicity of the proposed radiotherapy treatment), there are no data currently available from previous studies. In the absence of criteria useful for the sizing of the

sample in formal terms, the sample (12 cases) is defined according to criteria of opportunity and feasibility, with two steps of evaluation of the outcome as follows:

- after the first 3 patients enrolled and treated with the proposed radiotherapy scheme, there will be a 1 month stop in the enrollment of subsequent patients, in which tolerance and the occurrence of serious adverse events will be analyzed.
- At the end of the month, if none of the patients treated shows toxicity attributable to radiation treatment > 3, the enrollment of the next 3 patients will continue with a further stop in enrollment for another month.
- If these patients, together with the 3 previously treated, do not have serious adverse events induced by radiation treatment, the enrollment of the last 6 patients will continue.

All patients in the study will be followed, for the primary endpoint of the study, for at least 3 months from enrollment, or until disease progression or death from another cause.

At the end of each intermediate step, the investigator will produce a report on the safety of the cases already treated which will be subjected to the evaluation of an internal board, composed of the Health Director, the Scientific Director and the Legal Doctor of the ASMN-IRCCS of Reggio Emilia, who will express on the continuation / interruption of the study and subsequently notified to the EC.

The internal board will also evaluate any urgent safety measures (as defined in paragraph 11.4) transmitted by the RAV, expressing its opinion on the continuation / interruption of the study and subsequently notifying the EC of this opinion.

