2. RATIONAL OF THE STUDY

Relapsed GBMs have a life expectancy of a few months and reirradiation has been shown to be safe in terms of toxicity and effective in increasing OS. Our recent study Ciammella P. et al [94] reported a median survival of 9.5 months in patients affected by recurrent GBM and treated with stereotaxic radiotherapy with a total dose of 25 Gy in 5 consecutive sessions, in which the dose was prescribed at isodose of 70% with a homogeneous gradient towards the center of the target volume. The identification with functional imaging of specific areas with higher tumor cell density, and the possibility of accurately delivering, thanks to the most advanced therapy units, different doses to the different sub-volumes, can lead to an increase in the maximum deliverable dose. In the most aggressive areas (with a greater tumour killing effect), compared to lower doses in the areas with the lowest signal alteration. This dose selectivity should allow an increase in the efficacy of the therapy and therefore a hypothesized increase in local control, in the face of a radio-induced toxicity on surrounding healthy tissues almost comparable to that achieved with previous hypofractionated treatments [94]. In fact, delivering very high doses to the entire volume would lead to an excess of radio-induced necrosis within the regions irradiated with high doses, as well as the impossibility of minimizing the doses on healthy areas and / or on non-neoplastic critical areas, keeping them at internal dose range associated with minimum and acceptable toxicity levels. Since there are no studies that provide clear indications on the acute and late toxicity of irradiated healthy tissues, that have already been the subject of a first course of radiotherapy (STUPP), the choice of safety is the primary objective of the study.

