5. DESIGN OF THE STUDY

It is an exploratory, prospective, experimental, monocentric study.

Having identified a main safety endpoint (toxicity of radiotherapy treatment), and in the absence of data currently available from previous studies and useful for sample sizing, the sample is defined according to criteria of expediency and feasibility, (12 cases), with a design (3 cases + 3 cases + 6 cases) which provides for two intermediate safety assessment steps, one month after the end of treatment for the third and sixth patient. The study will be continued only in the event of a positive evaluation of both steps.

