5.2 Early termination of the study

An internal board will evaluate according to the analysis plan defined in section 12.1 the continuation / interruption of the study in the protection of patients' interests, based on information on the safety of the cases already treated.

The study can be concluded early:

- if the nature and frequency of the events and / or any urgent safety measures are such that the risk and benefit ratio is not acceptable;
- if the number of patients who drop out of the study is such that it is difficult to complete the study.

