6. TREATMENT PLAN

6.1 Radiotherapy treatment

The treatment envisaged by the protocol involves the planning and execution of a hypofractionated radiotherapy (RT) treatment, administered in 5 daily sessions, with modulated intensity technique and inhomogeneous distribution of the dose guided by diffusion images obtained with magnetic resonance imaging (MRI).

The radiotherapy treatment must begin within 7 days from the date of execution of the centering MRI which will include both the classic morphological sequences with administration of contrast medium and functional. In this regard, for more details see the Technical Annex.

In selected cases and according to clinical judgment, it will be possible to request a review of the anatomic-pathological and radiological findings.

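### Patient events reach the board by rule only after patients 3 and 6; a disqualifying event in patient 1, 2, 4 or 5 requires no hold or board notice in the visible text

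*Combined protocol and SAP*

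**What the plan says.** Section 5 plans "two intermediate safety assessment steps, one month after the end of treatment for the third and sixth patient". Section 12.1 gives the detail. The first pause comes "after the first 3 patients enrolled and treated with the proposed radiotherapy scheme, there will be a 1 month stop in the enrollment". Recruitment then resumes "if none of the patients treated shows toxicity attributable to radiation treatment > 3, the enrollment of the next 3 patients will continue". After a second one-month pause, the last six may enter if patients 4 to 6, "together with the 3 previously treated, do not have serious adverse events induced by radiation treatment". On reporting, 12.1 states: "At the end of each intermediate step, the investigator will produce a report on the safety of the cases already treated". The internal board then gives its view on continuing or stopping; 12.1 contains no automatic stop.

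Other sections also bear on safety between the pauses:

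- **5.2** allows early conclusion, for instance "if the nature and frequency of the events and / or any urgent safety measures are such that" the balance of risk and benefit is unacceptable. It ties the board's evaluation to the plan in 12.1.
- **6.7 and 7.2** stop the affected patient's own treatment.
- **10.2** asks for a CRF entry for a serious event.
- **10.3** provides a safety report as 12.1 lays down, and otherwise on request.
- **11 to 11.3** send safety reports to the Ethics Committee, and device incidents within 10 days to the device contact, the Ministry and the Ethics Committee.
- **11.4** passes manufacturer or authority notices about devices to the board.

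**The concern.** Both conditions are zero-event conditions, so the first qualifying event settles whether the condition is met, whichever patient has it. The plan nevertheless times the check by the last patient of each cohort. If patient 1 has a radiation-attributable toxicity above grade 3, the condition for opening the second cohort is already unmet, yet patients 2 and 3 may still start with the plan followed to the letter. The same holds for patients 5 and 6 after an event in patient 4. There the condition is the absence of radiation-induced serious adverse events, and section 10.1 counts fatal and life-threatening events as serious.

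What is at stake is avoidable exposure. The regimen gives 30 Gy, rising to at most 50 Gy, in five sessions to brain that has been irradiated before. Section 2 makes safety the primary objective because clear toxicity data for such tissue are lacking, and 12.1 says no earlier data on the main endpoint are available.

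**Working it through.** **Figure in the plan.** There is no statistical figure to reproduce. The sample of 12 (3 + 3 + 6) is declared a choice of feasibility. The check is first a reading of the clauses, then a scale for the consequence. I read the threshold in 12.1 as CTCAE grade above 3, in line with 6.7.

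**Clauses side by side.** For a patient event between the planned steps:

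| Section | Holds new starts? | Board must be told? |
|---|---|---|
| 5, 12.1 | only after patients 3 and 6 | only at the two steps |
| 5.2 | may end the study, at discretion | no separate trigger |
| 6.7, 7.2 | no, affected patient only | no |
| 10.2 | no | no, CRF entry |
| 10.3 | no | on request |
| 11 to 11.3 | no | no; device contact, Ministry, Ethics Committee |
| 11.4 | no | device notices only |

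**Maximum.** An event in the first patient of a cohort leaves two more to start before the check. Under the grade > 3 criterion the maximum per trial is also two if the study ends when step 1 fails, because an event in cohort 1 then prevents cohort 2.

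**Expected number, event known before the next start.** Assume an independent event probability p per patient, the same in both cohorts. Patient 2 starts after an event with probability p, and patient 3 with probability 1 − (1 − p)². Per cohort:

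e = p + [1 − (1 − p)²]

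Cohort 2 opens with probability (1 − p)³, so per trial the number is e × [1 + (1 − p)³]. At p = 10%: e = 0.10 + 0.19 = 0.29, and 0.29 × 1.729 = 0.50.

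**Expected number, late recognition.** Section 8.3 has visits at 30, 60 and 90 days after radiotherapy, and the endpoint in 4.1 runs to 3 months. The synopsis gives 22 months of enrolment. Less two one-month pauses, that is L = 12/20 = 0.6 patients per month, with random arrivals assumed. The delay d from start of treatment to recognition is the visit time plus 5 days (0.164 months).

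- S1 = exp(−Ld) is the chance that the next patient starts after recognition.
- S2 = S1 × (1 + Ld) is the same for the patient after that.
- Per cohort, c = p(2·S1 + S2) − p²·S1. Per trial, c × [1 + (1 − p)³].

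Day 30: d = 1.164, S1 = 0.497, S2 = 0.845. Day 90: d = 3.164, S1 = 0.150, S2 = 0.434. At p = 10% and day 90, c = 0.10 × 0.734 − 0.01 × 0.150 = 0.072, and 0.072 × 1.729 = 0.12.

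| p (assumed) | Known before next start | Known at day 30 | Known at day 90 |
|---|---|---|---|
| 2% | 0.12 | 0.07 | 0.03 |
| 5% | 0.27 | 0.17 | 0.07 |
| 10% | 0.50 | 0.31 | 0.12 |
| 20% | 0.85 | 0.53 | 0.21 |
| 30% | 1.09 | 0.68 | 0.28 |

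The 51-month enrolment of section 5.1 raises the late-recognition figures, because events have longer to surface before the next start. At p = 10% and day 30 the figure becomes 0.41.

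**Limit of the day-90 column and of the maximum.** Both count only later patients of the same cohort and suppose that step 1 sees every cohort 1 event. An event in patient 3 that surfaces at day 90 comes two months after step 1. With L × 2 = 1.2, patients 4, 5 and 6 start after it with probability exp(−1.2) = 0.30, 0.301 × 2.2 = 0.66 and 0.301 × 2.92 = 0.88, together 1.84. At p = 10%, with no event in patients 1 and 2, this adds 0.10 × 0.81 × 1.84 = 0.15, giving 0.12 + 0.15 = 0.27. In that case all three of patients 4 to 6 could start after the event is known. The day-90 column is therefore a same-cohort count, not a floor.

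**The case against.** Reviewing by cohorts of three, with discretion to stop at any time under 5.2, is a defensible choice in a 12-patient exploratory study. A careful investigator would probably pause without being told to. Section 11.1 counts unexpected adverse reactions among device incidents and presumes a device contribution in difficult cases, and 11.2 sets a 10-day limit. Section 13.3 promises continuous availability of CRF data and centralised monitoring, and the board is drawn from the sponsoring institution. Sections 11 and 13.1 also adopt a serious-event reporting guideline, a company procedure, GCP and ISO 14155. Section 1 reports low toxicity in earlier re-irradiation series, which favours the low rows of the table even though the regimens differ.

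Most of this is fair, and it limits the size of the point. It does not supply the missing duty: none of the visible clauses holds new starts or puts a patient event before the board between steps. The texts of the guideline, procedure and standards are not in the documents, so whether a duty exists there remains open.

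A reader might infer that five patients could be exposed, since a radiation-induced grade 3 hospitalisation in patient 1 satisfies the step 1 criterion but not the pooled step 2 criterion. The documents do not support that as a result of the missing hold. Section 12.1 has serious adverse events analysed during the first pause, and the board gives its view before patients 4 to 6 start. What remains there is a difference between the two criteria, which is a separate matter.

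**Conclusion.** The point stands, at moderate weight. The visible plan lets up to two further patients per cohort be re-irradiated after its own condition for continuing is unmet and before the board has looked. Depending on how soon events are recognised, the expected same-cohort excess per trial is 0.03 to 0.12 patients at p = 2% and 0.28 to 1.09 at p = 30%. It is small if severe toxicity is rare. These figures rest on an assumed rate, independent patients, one p for both cohorts, the stated accrual pattern, and a study that ends if step 1 fails.

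Two stronger readings should be avoided. The plan does not leave serious events unreported, because section 11 has external routes and 10.3 lets the board ask. Nor does it forbid stopping early; it only fails to require a pause. The calculation concerns patients 1 to 6, since 12.1 sets no further step for patients 7 to 12.

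**What to change.** In 12.1, state that before each planned step the first radiation-attributable toxicity above grade 3 in any patient suspends new starts of irradiation and triggers an immediate safety report. During patients 4 to 6, the first radiation-induced serious adverse event does the same. No new patient starts until the board has given an expedited opinion. In 10.2, require such events to be sent to the board within a stated short deadline. These triggers follow the protocol's own criterion for each step, and the decision stays with the board. Using any serious event as a trigger in patients 1 to 3 would tighten the step 1 criterion, and is not proposed here.

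The cost is a sentence in each section, a board that can meet between steps, and an occasional short pause. With one p for both triggers, the chance of a first event in patient 1, 2, 4 or 5, and so of a hold the plan does not already have, is [1 − (1 − p)²] × [1 + (1 − p)³]: 8%, 18%, 33%, 54% and 68% at the five assumed rates. It would be higher if serious events in the second cohort are commoner than toxicity above grade 3.

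Section 6.1 says "The radiotherapy treatment must begin within 7 days from the date of execution of the centering MRI", so a hold may force a repeat MRI and replanning for a patient already imaged. If imaging is a full 7 days ahead, this affects about 1 − exp(−0.6 × 7/30.4) = 13% of holds with 22-month enrolment, or about 5% with 51 months. Section 2 notes: "Relapsed GBMs have a life expectancy of a few months". The review must therefore be quick, and the text should say so.

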10.1 Evaluation of adverse events from radiotherapy

An adverse event (AE) is any adverse clinical event that occurs in a patient or clinical trial subject receiving treatment and which does not necessarily have a causal relationship to that treatment. An adverse event can occur in the treatment period and in the follow-up period.

An adverse event is defined as SERIOUS (SAE) if it has:

- lethal outcome;
- endangers the patient's life (it means that in the Investigator's opinion the patient is at immediate risk of death);
- imposes a hospitalization or extends the hospitalization in progress following the procedures provided for in the protocol;
- involves severe or prolonged disability or incapacity, a congenital anomaly or malformation or a birth defect;
- may endanger the subject or require intervention to prevent one of the above situations.

Within the protocol, hospitalizations already planned before the start of the protocol or as parts of the protocol, hospitalizations lasting less than 24 hours or occurring in the absence of an adverse event will not be considered serious adverse events.

For each adverse event (AE), the Investigator will provide information on the nature of the event, severity, start and end date, actions taken, causation with the treatment, seriousness and outcome.

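### Section 12.1 judges patients 1–3 by one go criterion at step 1 and a different one at step 2, so an event known at the first stop can pass step 1 yet already fail step 2

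*Combined protocol and SAP*

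**What the plan says.** The study enters 12 patients as 3 + 3 + 6, with an enrolment pause after the third and after the sixth patient.

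- **First pause (section 12.1).** This is a one-month stop "in which tolerance and the occurrence of serious adverse events will be analyzed". Patients 4–6 are then opened "if none of the patients treated shows toxicity attributable to radiation treatment > 3".
- **Second pause (section 12.1).** Patients 7–12 are opened if patients 4–6, taken together with the first three, "do not have serious adverse events induced by radiation treatment, the enrollment of the last 6 patients will continue".
- **Board (section 12.1).** After each step the investigator's safety report goes to an internal board, "who will express on the continuation / interruption of the study".
- **Overall condition (section 5).** "The study will be continued only in the event of a positive evaluation of both steps". Section 5 does not define a positive evaluation.
- **Early termination (section 5.2).** The board "will evaluate according to the analysis plan defined in section 12.1 the continuation / interruption of the study". A general clause also allows early closure if the events "are such that the risk and benefit ratio is not acceptable".
- **Seriousness (section 10.1).** An event is serious if, among other routes, it "imposes a hospitalization or extends the hospitalization in progress". Planned hospital stays and stays under 24 hours are excluded. Severity and seriousness are listed as separate items to record for each event.
- **Severity (section 10.1.1).** Events are graded 1 to 5 on CTCAE version 4.0.

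**The concern.** Patients 1–3 are assessed twice, on different scales: by severity at step 1 and by seriousness at step 2. If the two scales can disagree, the same event in the same patient can count as a go at the first stop and a no-go at the second, with nothing new having happened.

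Safety is the primary objective, and these are the only step-specific go/no-go criteria in the plan. At stake is whether up to three further patients could receive experimental re-irradiation when the written condition for continuing the study has already become unattainable.

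**Working it through.** **1. Sample size.** The only figure to reproduce is 3 + 3 + 6 = 12, which agrees. Section 12.1 says the number was set by opportunity and feasibility, so there is no error rate or power to check.

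**2. Do the criteria differ?** The step-1 wording omits the word grade. Sections 6.7 and 7.2 write grade > 3 in full, and section 10.1.1 uses a 1–5 scale, so the natural reading is grade 4 or 5. Section 10.1 makes an event serious through hospitalisation, disability or a need for preventive intervention, without reference to grade. A radiation-induced grade 3 event that leads to an unplanned hospital stay of 24 hours or more is thus not > 3, but is an SAE.

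**3. Outcomes for patients 1–3.** Give each patient one of three states:
- N: no radiation-induced SAE.
- S: radiation-induced SAE of grade 3 or lower.
- G: attributable toxicity > 3, taken here to be an SAE.

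Of the 3³ = 27 patterns, 2³ = 8 contain no G and pass step 1. Seven of those 8 contain at least one S and so already fail step 2; only N-N-N leaves step 2 attainable. These are counts of patterns, not probabilities.

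**4. Probability under assumed rates.** The documents give no rates. Let g be the assumed per-patient rate of attributable toxicity > 3 by the first stop, and s the rate of any radiation-induced SAE, with s including g. Treat patients as independent.

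P(step 1 passed, step 2 already failed) = (1 − g)³ − (1 − s)³

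| g / s | (1 − g)³ | (1 − s)³ | Probability | Expected patients 4–6 treated in this situation (3 × probability) |
|---|---|---|---|---|
| 5% / 5% | 0.8574 | 0.8574 | 0% | 0 |
| 2% / 5% | 0.9412 | 0.8574 | 8.4% | 0.25 |
| 5% / 10% | 0.8574 | 0.7290 | 12.8% | 0.39 |
| 5% / 20% | 0.8574 | 0.5120 | 34.5% | 1.04 |

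The result is zero when every radiation-induced SAE is also > 3, and grows with the share of SAEs at grade 3 or lower. All figures apply the literal criteria, before any board discretion.

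**The case against.** The strongest reply is that the step-1 criterion does not act alone. SAEs are analysed in the first pause, the investigator reports to the board, and the board can interrupt the study there or invoke the risk/benefit clause of section 5.2. An SAE in patients 1–3 would be in front of the board before patients 4–6 are opened. This stands, and it lowers the practical risk. It does not close the gap: the go condition that follows the SAE analysis does not mention SAEs, nothing obliges the board to stop, and section 5.2 sends the board back to section 12.1 for its rule.

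A second reply is that a severity criterion before three patients and a stricter cumulative one before six can coexist. That also stands. A reader might infer that section 12.1 contradicts itself and cannot be operated, but both rules can be applied exactly as written. What is missing is coherence in one contingency. Nor would data from patients 4–6 be lost, since section 13.4 commits to publication even after early interruption.

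A third reply is that the text is a translation and serious may have been meant as severe. This cannot be excluded, but section 10.1 defines an SAE independently, so the current text does not support that reading. If it was the intent, the wording still needs correcting.

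Two further inferences should be resisted:
- The five-level scale in section 10.1.1 does not prove the overlap. It covers only events outside CTCAE, and it names hospitalisation at level four, which is already > 3. The overlap rests on section 10.1.
- The table does not show that the situation is likely. The rates are assumed, and nothing in the documents supports an SAE rate of 20% by the first stop.

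**Conclusion.** The point holds as an inconsistency in the go/no-go rules. A radiation-induced SAE of grade 3 or lower in patients 1–3, known at the first stop, meets the written step-1 criterion and by itself fails step 2. Patients 4–6 could then be treated although the section 5 condition of two positive evaluations is out of reach on the written criteria.

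Its extent is limited: one contingency, at most three patients, after a mandatory pause and a board review. Its probability is unknown. The illustrative range of 0% to 34.5% rests on assumed rates, independence between patients, every attributable toxicity > 3 being an SAE, and no board intervention. The inconsistency itself depends only on reading > 3 as a grade and on the SAE definition in section 10.1. It merits correction because it concerns a decision rule that governs patient exposure in a study whose primary objective is safety.

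**What to change.** Reconcile the step-1 and step-2 criteria in section 12.1, and align sections 5 and 5.2, so that an event known at step 1 cannot pass step 1 and by itself fail step 2. State that > 3 refers to grade, if that is meant. The choice of criterion belongs to the sponsor.

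The cost is an amendment of a few lines, with no added patients. The statistical consequence depends on the choice, under the same assumed rates and ignoring SAEs that appear in patients 1–3 only after the first stop:

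- **SAE criterion at both steps.** The chance of passing step 1 falls from (1 − g)³ to (1 − s)³: from 85.7% to 72.9% at 5%/10%, and to 51.2% at 5%/20%. The chance of reaching patient 7 stays at (1 − s)⁶, which is 53.1% and 26.2%, because step 2 already counts patients 1–3 again.
- **Criterion > 3 at both steps.** The chance of passing step 1 stays at 85.7% when g = 5%. The chance of reaching patient 7 becomes (1 − 0.05)⁶ = 73.5%, and the study would continue despite SAEs of grade 3 or lower.
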